KEYNOTE-012 study data showed that the ORR in PD-L1 positive gastric cancer subjects is about 22% (Muro 2016). Since subjects will not be selected based on PD-L1 expression levels prospectively in this study, in order to accommodate all subjects (irrespective of PD-L1 expression levels), a conservative ORR of 15% is assumed with pembrolizumab treatment alone and it is further assumed that the addition of PEGPH20 to pembrolizumab will lead to a clinically meaningful improvement of 20% in ORR to 35%. Under these assumptions, 21 subjects will provide approximately 80% power at the hypothesized ORR of 35% when the null hypothesis H0: ORR ≤15% tested against H1: ORR >15% using an exact one sided binomial test at a 10% significance level.

Analysis Populations

Safety Population: All subjects who receive any study medication. The Safety Population will be used for subject disposition, demographics and safety analyses.

DLT Evaluable Population: All subjects who receive at least 1 of the 3 full planned doses of PEGPH20 and 1 complete dose of pembrolizumab in Cycle 1 and have been followed for the first 21 days of treatment or have experienced a DLT during the initial 21 days (Cycle 1) of the study. The DLT Evaluable Population will be used for DLT analysis.

PK Analysis Population: All subjects who receive any PEGPH20 and have measurable PEGPH20 concentrations in at least 1 sample collected for PK analysis. PK Analysis Population will be used for PK analysis.

Efficacy Evaluable Population: All HA-high subjects who receive at least 1 dose of the RP2D of PEGPH20 and at least 1 dose of pembrolizumab. The efficacy evaluable population will be used for all efficacy analyses.

Tumor Response Evaluable Population: Subjects in the Efficacy Evaluable Population who have at least one post-baseline tumor assessment. Tumor Response Evaluable Population will also be used for overall tumor response analysis.

Analyses

Analysis of Demographics and Baseline Characteristics

Demographics and baseline characteristics will be summarized using safety population by dose level for subjects in the Dose Escalation portion and separately for all subjects in the Dose Expansion portion. The following demographic and baseline characteristics will be summarized: age, race, height, weight, medical history, disease characteristics, and treatment history.

Efficacy Analyses

All efficacy analyses will be conducted using the Efficacy Evaluable Population. ORR and DOR will also be analyzed using Tumor Response Evaluable population.

The primary efficacy endpoint of the study is PEGPEM treatment effect on ORR based on RECIST v1.1. The statistical hypothesis tests for the primary endpoint are as follows:

- NSCLC cohort: H₀: ORR ≤23%; H₁: ORR >23%
- Gastric adenocarcinoma cohort: H₀: ORR ≤15%; H₁: ORR >15%

The hypothesis tests will be conducted using the one-sided exact binomial test at the significance level of 0.1.

ORR will be calculated as the number of subjects with a confirmed CR or PR divided by the number of subjects in the analysis population multiplied by 100. The exact 80% confidence interval of ORR will also be constructed. DCR and its exact 80% CI will be calculated. Median DOR, PFS and OS and their corresponding 80% confidence intervals will be estimated using the Kaplan-Meier method.

Safety Analyses

All safety parameters will be summarized using the Safety Population.

All AEs will be presented in incidence tables coded by the Medical Dictionary for Regulatory Activities (MedDRA) Preferred Term and System Organ Class. Additionally, separate AE incidence tables, coded by MedDRA term, will be presented by: 1) toxicity grade (severity) graded by the CTCAE and 2) relationship to study medication (PEGPH20 and pembrolizumab).

All AEs, serious adverse events, AEs leading to treatment discontinuation, and deaths occurring during the study will be summarized.

Laboratory parameters and vital signs and the corresponding change from baseline over time will be summarized using descriptive statistics.

Pharmacokinetic and Pharmacodynamic Analyses

For PEGPH20 noncompartmental and compartmental PK modeling will be performed. The AUC, the C_{max} and $T_{1/2}$ will be summarized from noncompartmental analysis along with descriptive statistics. Other PK analyses may be performed and population PK parameters including $T_{1/2}$, V_D , and CL will be evaluated and reported if the data are sufficient. For plasma HA, descriptive statistics will be used to summarize the measured plasma concentrations.

Exploratory Analyses

Descriptive summaries will be provided for all exploratory endpoint analyses.

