 - b. **Dose Expansion portion -** Available tumor tissue in FFPE block or 10-15 unstained consecutive tumor tissue slides from 1 tumor tissue block that meet specific tissue sample requirements are mandatory. **Note:** Fine needle aspirates or brushing biopsies will not be acceptable. Archived resection specimens from the primary tumor without radiologic evidence of metastasis at the time of resection are not suitable to establish histological confirmation and require new tumor tissue of a metastatic site.
- 5. To be eligible for the Dose Escalation portion, subjects need only have evaluable disease (details in Section 8.2.15); to be eligible for the Dose Expansion portion, subjects must

have measurable disease per RECIST v1.1. Previously irradiated tumors may be eligible if they have clearly progressed in size.

- 6. ECOG Performance Status of 0 or 1.
- 7. Life expectancy ≥ 3 months.
- 8. Males and females aged \geq 18 years.
- 9. Resolution of all acute toxic effects of prior therapy or surgery to baseline.
- 10. Screening clinical laboratory values are as follows:
 - a. Total and indirect bilirubin \leq 1.5 × upper limit of normal (ULN), except for Gilbert's syndrome
 - b. Aspartate aminotransferase (AST), alanine aminotransferase (ALT), and alkaline phosphatase (ALP) $\leq 2.5 \times \text{ULN}$ ($\leq 5 \times \text{ULN}$ is allowed if liver metastases are present)
 - c. Serum creatinine ≤1.5 mg/dL or calculated creatinine clearance ≥40 mL/min
 - d. Serum albumin ≥3.0 g/dL
 - e. Hemoglobin ≥10 g/dL (transfusion and erythropoietic agents allowed)
 - f. Absolute neutrophil count ≥ 1500 cells/mm³
 - g. Platelet count $\geq 100,000/\text{mm}^3$
- 11. Female participants of childbearing potential (WOCBP) must have a negative urine or serum pregnancy test within 7 days before Day 1 (first dose of study medication).
- 12. For WOCBP and for men, agreement to use an effective contraceptive method from the time of screening throughout the study until 4 months (WOCBP) or 3 months (men) after administration of the last dose of any study medication. Highly effective contraceptive methods consist of prior sterilization, intrauterine device (IUD), intrauterine hormone releasing system (IUS), oral or injectable contraceptives, and/or barrier methods. Abstinence alone is not considered an adequate contraceptive measure for the purposes of this study.

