 - b. **Dose Expansion portion -** Available tumor tissue in FFPE block or 10-15 unstained consecutive tumor tissue slides from 1 tumor tissue block that meet specific tissue sample requirements are mandatory. **Note:** Fine needle aspirates or brushing biopsies will not be acceptable. Archived resection specimens from the primary tumor without radiologic evidence of metastasis at the time of resection are not suitable to establish histological confirmation and require new tumor tissue of a metastatic site.
- 5. To be eligible for the Dose Escalation portion, subjects need only have evaluable disease (details in Section 8.2.15); to be eligible for the Dose Expansion portion, subjects must have measurable disease per RECIST v1.1. Previously irradiated tumors may be eligible if they have clearly progressed in size.
- 6. Eastern Cooperative Oncology Group (ECOG) Performance Status of 0 or 1 (Appendix B).
- 7. Life expectancy ≥ 3 months.
- 8. Males and females aged \geq 18 years.
- 9. Resolution of all acute toxic effects of prior therapy or surgery to baseline.
- 10. Screening clinical laboratory values are as follows:
 - a. Total and indirect bilirubin $\leq 1.5 \times$ upper limit of normal (ULN), except for Gilbert's syndrome
 - b. Aspartate aminotransferase (AST), alanine aminotransferase (ALT), and alkaline phosphatase (ALP) $\leq 2.5 \times \text{ULN}$ ($\leq 5 \times \text{ULN}$ is allowed if liver metastases are present)
 - c. Serum creatinine ≤1.5 mg/dL or calculated creatinine clearance ≥40 mL/min
 - d. Serum albumin >3.0 g/dL
 - e. Hemoglobin ≥10 g/dL (transfusion and erythropoietic agents allowed)
 - f. Absolute neutrophil count ≥1500 cells/mm³
 - g. Platelet count $\geq 100,000/\text{mm}^3$
- 11. Female participants of childbearing potential (WOCBP) must have a negative urine or serum pregnancy test within 7 days before Day 1 (first dose of study medication).
- 12. For WOCBP and for men, agreement to use an effective contraceptive method from the time of screening throughout the study until 4 months (WOCBP) or 3 months (men) after administration of the last dose of any study medication. Highly effective contraceptive methods consist of prior sterilization, intrauterine device (IUD), intrauterine hormone releasing system (IUS), oral or injectable contraceptives, and/or barrier methods. Abstinence alone is not considered an adequate contraceptive measure for the purposes of this study.

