8.2.2. Inclusion/Exclusion Criteria

The inclusion/exclusion criteria (Sections 7.1 and 7.2) must be reviewed at screening to ensure that the subject qualifies for the study. Subjects may be enrolled into the study if all selection criteria are met.

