8.2.13. Contraception

Highly effective methods of contraception for participating WOCBP should be used during the study treatment and up to 4 months following the last dose of any study medication, and include the following:

- Combined (estrogen and progestogen containing) hormonal contraception associated with inhibition of ovulation (oral, intravaginal, transdermal)
- Progestogen-only hormonal contraception associated with inhibition of ovulation (oral, injectable, implantable)
- Intrauterine device
- Intrauterine hormone-releasing system
- Bilateral tubal occlusion
- Vasectomized partner

Participating men can be fertile or vasectomized. Fertile men are advised to use effective methods of contraception during the study and until 3 months after administration of the last dose of any study medication.

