10.7. Pregnancy

Pregnancy itself is not regarded as an AE unless there is suspicion that the study drug may have interfered with the effectiveness of the contraceptive medication. Refer to the pembrolizumab Prescribing Information for the summary of risks in this specific population. Based on its mechanism of action, pembrolizumab can cause fetal harm when administered to a pregnant woman. Women of childbearing potential should therefore use highly effective contraception during treatment with pembrolizumab and refrain from breast feeding for 4 months after the last dose of pembrolizumab. Pregnancy within 120 days of study drug discontinuation in a subject must be reported to the designated safety contact (contact information is provided in the study reference binder) **IMMEDIATELY AND NO LATER THAN 24 HOURS OF**

AWARENESS. Complete the study-specific Pregnancy Report Form with all available information and submit the form with pregnancy test results and any other pertinent information. Also, within 24 hours, complete the eCRF with all available AE, demographic, medical history, concomitant medication, and study drug administration information. As additional information on a previously reported pregnancy becomes available, a follow-up Pregnancy Report Form should be prepared with the new information and submitted to the safety contact.

Subjects who become pregnant during the study will not receive any additional study drug and will be withdrawn from the study. The Investigator must strongly encourage these subjects to return to the study site for the final protocol-specified visit and assessments. In addition, the Investigator will monitor the pregnancies of subjects exposed to study drug or the partner of a male subject who may become pregnant while that subject is on study until final resolution (delivery, miscarriage, or early termination). Follow-up should occur monthly and should be documented in the study file. A follow-up Pregnancy Report Form must be completed for each follow-up contact with the subject or the partner of a male subject who became pregnant while that subject is on study and submitted to the Sponsor's designated safety contact. Report a spontaneous miscarriage, therapeutic abortion, stillbirth, or congenital anomaly as an SAE (Section 10.3).

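### Inclusion criterion 12 lets a woman of childbearing potential enrol on a barrier method alone, although Section 8.2.13 names no barrier method among its highly effective methods for women

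*Protocol*

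**What the plan says.** Criterion 12 appears in the Synopsis and again in Section 7.1. It requires "agreement to use an effective contraceptive method from the time of screening throughout the study until 4 months (WOCBP) or 3 months (men") after the last dose. It then defines the better tier of methods in a single list, not divided by sex: "Highly effective contraceptive methods consist of prior sterilization, intrauterine device (IUD), intrauterine hormone releasing system (IUS), oral or injectable contraceptives, and/or barrier methods". Section 7.1 ends its list the same way, with "oral or injectable contraceptives, and/or barrier methods". One exclusion follows: "Abstinence alone is not considered an adequate contraceptive measure for the purposes of this study".

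Section 8.2.2 makes the criteria the test for entry: "Subjects may be enrolled into the study if all selection criteria are met". Section 12.1.1 rules out waivers of the criteria.

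Section 8.2.13 treats the sexes separately. For women it states that "Highly effective methods of contraception for participating WOCBP should be used during the study treatment", and for up to 4 months "following the last dose of any study medication, and include the following". Six methods are then named: combined hormonal, progestogen-only hormonal, intrauterine device, intrauterine hormone-releasing system, bilateral tubal occlusion and a vasectomized partner. Fertile men are advised to use effective methods until 3 months after the last dose.

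Section 10.7 gives the reason for the stricter standard in women: "pembrolizumab can cause fetal harm when administered to a pregnant woman". It asks WOCBP to use highly effective contraception but names no methods.

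**The concern.** Sites enrol against the numbered criteria. If the criterion accepts a method that the protocol's own section for WOCBP does not name as highly effective, a woman can be entered correctly on less protection than Sections 8.2.13 and 10.7 appear to intend. The combination includes a drug that the protocol says can cause fetal harm.

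A site looking for guidance would not find the point settled elsewhere. Neither Section 8.2.13 nor Section 10.7 says that a barrier method alone is insufficient, and criterion 12 expressly calls barrier methods highly effective.

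**Working it through.** The point rests on wording and no calculation applies, so the texts are set side by side.

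| Question | Criterion 12 (Synopsis, Section 7.1) | Section 8.2.13 | Section 10.7 |
|---|---|---|---|
| Who is covered | WOCBP and men in one rule | WOCBP and men separately | WOCBP |
| Standard for WOCBP | Effective | Highly effective | Highly effective |
| Standard for men | Effective | Effective (advised, if fertile) | None given |
| Start for WOCBP | Screening | Study treatment | Pembrolizumab treatment |
| Methods named for WOCBP | Shared list, barrier methods included | Six, no barrier method | None |
| Ruled out as sole measure | Abstinence | None stated | None stated |

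**Step 1: does a WOCBP using a barrier method alone pass criterion 12?** The rule asks for an effective method. Barrier methods are on its list of highly effective methods, and the connective *and/or* lets each item stand alone. The only excluded sole measure is abstinence. She passes.

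**Step 2: is the list limited by sex?** The rule opens by naming both sexes, and the list contains intrauterine methods, which only women can use, so it was not written for men alone. Nothing assigns the barrier entry to men.

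**Step 3: is it a slip in the Synopsis only?** No. Section 7.1 carries the same list.

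**Step 4: does Section 8.2.13 name a barrier method for WOCBP?** No. None of its six methods is one.

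**Step 5: does Section 8.2.13 contradict criterion 12?** Not strictly. Its list is introduced with *include*, so it is not expressly complete and does not reject barrier methods. Criterion 12 uses *consist of*, which defines a set. The two lists differ on one class of method, and nothing in the protocol or SAP says which governs.

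**Step 6: would deleting the barrier entry be enough?** No. The criterion's operative demand is only for an effective method, so the standard for WOCBP also has to be raised to highly effective.

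**The case against.** The strongest case on the other side has four parts.

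**The lists can be reconciled.** An open list that omits an item does not contradict a closed list that contains it, and Section 10.7 names no methods. A reader might infer that the protocol contradicts itself outright; the documents do not support that. Nor do they give failure rates or say that a barrier method is less than highly effective. What stands is narrower: the section written for WOCBP names no barrier method, and the entry rule accepts one alone.

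**Later sections still apply.** Sections 8.2.13 and 10.7 bind after enrolment, so it would be wrong to infer that the protocol lacks a standard for women. There are other safeguards too: a negative test within 7 days before Day 1, a test at the start of each cycle from Cycle 2 (Section 8.2.12), immediate discontinuation on pregnancy (Section 7.3.1), and reporting of a pregnancy within 120 days of stopping study drug (Section 10.7). These detect a pregnancy and limit further exposure. They do not prevent it, and they do not correct the entry rule.

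**The barrier entry was probably meant for men.** That is plausible, but the text does not say so.

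**Enrolment has ended.** SAP Section 4.7.2 records the decision of 31 May 2018 to stop enrolling. The point therefore concerns the rule under which subjects entered.

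A reader might also try to size the problem from the testing schedule: one pembrolizumab and three PEGPH20 doses fall due between tests, over 21 days, or up to 7 + 21 = 28 days for the first interval. Those figures are the same whatever method a woman uses, and the fix would not alter them. They do not measure this defect.

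**Conclusion.** The point holds as a mismatch between the eligibility rule and the section for WOCBP. As written, a WOCBP using only a barrier method satisfies criterion 12, while the section meant for her names six other methods and no barrier method.

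Its size cannot be estimated, because the documents give neither the number of WOCBP nor any failure rates. Endpoints, analysis populations, sample size and analysis are unaffected.

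The conclusion rests on reading *and/or* as letting each listed item stand alone, and on sites applying the criteria literally. It does not rest on any outside ranking of contraceptive methods. Priority is low to moderate: a safety wording correction to a rule that, when followed, gives the less protective result.

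**What to change.** Replace criterion 12 in the Synopsis and Section 7.1 with text to this effect:

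> WOCBP must agree to use a highly effective method listed in Section 8.2.13 from screening until 4 months after the last dose of any study medication; barrier methods may be used only in addition. Men who are not sterilized must agree to use an effective method, which may be a barrier method, from screening until 3 months after the last dose of any study medication; prior vasectomy is accepted.

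Keep the sentence on abstinence.

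Align Section 8.2.13 in three respects: start the WOCBP requirement at screening, state that its list governs for WOCBP, and make the rule for fertile men mandatory instead of advisory. Without these changes, criterion and section would still differ on start date and on how firmly men are bound.

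The cost is wording in three places plus any matching consent text. There are two consequences. A WOCBP relying on a barrier method alone would have to change or add a method to enrol. Making the list governing also closes a list that is now open, so other methods would no longer be accepted for WOCBP. Hormonal methods, both intrauterine methods, tubal occlusion and a vasectomized partner remain available. With enrolment closed, the criterion change cannot alter who entered; it matters for any protocol that reuses this text.

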3. STUDY SCHEDULES OF EVENTS

Table 1: Study Schedule of Events: Screening (Dose Escalation and Expansion)

To do and American	Screening
Tests and Assessments	≤28 Days Prior to Day 1
Sign and Date Informed Consent (Subject may provide consent for HA testing of tumor tissue on a separate, prescreening ICF in Dose Expansion [details in Section 8.2.1.1]) ^a	X
Study Procedure-Associated SAE Recording	X
Inclusion/ Exclusion Criteria	X
Medical History	X
Prior Medication History	X
Confirm and Retrieve Tumor Tissue ^b	X
Disease Assessment (CT scan/MRI scan of chest, abdomen, pelvis, and other areas of known or newly suspected disease) ^c	X
CT/MRI Brain scan to assess potential CNS disease and/or metastases	X
PET/CT ^d	X
DCE-MRI ^d	X
12-Lead ECG	X
Subject Registration into Interactive Web Response System following signing of ICF/prescreening ICF (if used in Dose Expansion)	X
Physical Examination ^c	X
Vital Signs ^c	X
ECOG Performance Status	X
Height ^c	X

 Table 1:
 Study Schedule of Events: Screening (Dose Escalation and Expansion) (Continued)

	Screening
Tests and Assessments	≤28 Days Prior to Day 1
Weight ^c	X
Urine/Serum Pregnancy Tests (WOCBP) (Local Laboratory) ^e	X
Central Laboratory Assessments	
Plasma HA Level and Exploratory Biomarkers	X
Hematology, Chemistry (Including Glucose), Urinalysis	X
Thyroid Function Tests ^f	X
Coagulation Tests	X

Abbreviations: CT = computed tomography; DCE-MRI = dynamic contrast-enhanced magnetic resonance imaging; ECG = electrocardiogram; ECOG = Eastern Cooperative Oncology Group; HA = hyaluronan; PET = positron emission tomography; T3 = triiodothyronine; T4 = total thyroxine; TSH = thyroid stimulating hormone; WOCBP = women of childbearing potential; CNS = Central Nervous System; ICF = Informed Consent Form; SAE = Serious Adverse Event

Note: Each treatment cycle is 21 days. Dose interruption and modifications are permitted.

In Dose Expansion – Available tissue from the primary or a metastatic lesion is required. An FFPE block or 10-15 unstained, consecutive tumor tissue slides of 1 tumor tissue block (refer to Inclusion Criterion #4 for more details) are required to send to the central laboratory. **Note:** Fine needle aspirates or brushing biopsies will not be acceptable. Archived resection specimens from the primary tumor without radiologic evidence of metastasis at the time of resection are not suitable to establish histological confirmation and require new tumor tissue of a metastatic site. Tumor tissue must be sent to central laboratory to assess HA status for eligibility into the Dose Expansion portion of the study.

^a The 28-day screening window will begin when the subject signs the study ICF (i.e., signature on the prescreening ICF does not initiate the screening window). ^b In Dose Escalation – Available tissue from the primary or a metastatic lesion is required. A formalin-fixed paraffin-embedded (FFPE) block or 5-10 unstained, consecutive core biopsy slides of 1 tumor tissue block (refer to Inclusion Criterion #4 for more details) are required to send to the central laboratory. **Note:** Fine needle aspirates or brushing biopsies will not be acceptable.

^c If these procedures are performed as part of standard-of-care prior to the subject's signing of the Informed Consent Form, the results may be used for screening purposes provided the procedures were performed within the screening window.

d Optional procedure. PET/CT and DCE-MRI scans will be sent to the Central Imaging Vendor for analysis if they are conducted. DCE-MRI scans must be obtained within 14 days prior to Day 1 (first dose of study medication).

^e To be performed within 7 days prior to Day 1 (first dose of study medication).

^f Blood samples will be collected for baseline testing of thyroid hormones (free T3, free T4; and TSH).

Table 2: Study Schedule of Events: PEGPH20 Plus Pembrolizumab Treatment (Cycles 1 and Beyond)

Tests and Assessments ^a	Tı	·eatmei	nt Cycle	1 (3 We	eks)		eatment ond (Re 3 W			28 Day Confirmatory CT Scan/MRI Scan	End of Treatment ^b	Long-Term Follow-up ^c
	Wk 1		Wk 2		/k 3		/k 1	Wk 2	Wk 3			
	D1	D2	D8	D15	D18	D1	D2	D8	D15			
Confirm Eligibility Based on Inclusion/ Exclusion Criteria	X											
Physical Examination											X	
Vital Signs ^d	X		X	X		X		X	X		X	
ECOG Performance Status	X					X					X	
Weight	X					X						
12-Lead ECG ^e											Xe	
Disease Assessment – CT/MRI Scan ^f									X ^f		X^g	
Response Confirmation Scan	_									X ^h		
CT/MRI Brain scan ⁱ									X ⁱ			
PET/CT Scan ^j (Optional at Selected Sites)					X				X			

Table 2: Study Schedule of Events: PEGPH20 Plus Pembrolizumab Treatment (Cycles 1 and Beyond) (Continued)

Tests and Assessments ^a	Tı	reatmei	nt Cycle	1 (3 We	eks)	Tro Bey	ond (Re	Cycle 2 epeats Eveeks)	and very	28 Day Confirmatory CT Scan/MRI Scan	End of Treatment ^b	Long-Term Follow-up ^c
	Wk 1		Wk 2	Wk 3		Wk 1		Wk 2	Wk 3			
	D1	D2	D8	D15	D18	D1	D2	D8	D15			
DCE-MRI ^k (Optional at Selected Sites)		X			X							
Urine/serum pregnancy test (local laboratory) before Dosing (WOCBP)						X						
Central Laboratory A	Assessm	ents										
Hematology	X		X	X		X		X	X		X	
Blood Chemistry (Includes Glucose)	X ^l		X ^l	X ^l		X ^l					X	
Blood Glucose								X	X			
Thyroid Function Tests ^m						X						
Coagulation Tests	X					X					X	
Immunogenicity ⁿ	X					X					X	
PK, HA and Other Biomarker Analyses	Refer	Refer to Table 3 for schedule of PK and biomarker sampling time points										
Optional Post-dose Tumor Biopsy					Xº							

Table 2: Study Schedule of Events: PEGPH20 Plus Pembrolizumab Treatment (Cycles 1 and Beyond) (Continued)

Tests and Assessments ^a	Tı	reatmei	nt Cycle	1 (3 We	eks)	Treatment Cycle 2 and Beyond (Repeats Every 3 Weeks)				28 Day Confirmatory CT Scan/MRI Scan	End of Treatment ^b	Long-Term Follow-up ^c
	Wk 1		Wk 2 Wk 3			Wk 1		Wk Wk 2 3				
	D1	D2	D8	D15	D18	D1	D2	D8	D15			
Piroxicam and Proton Pump Inhibitor Administration ^p	X		X	X		X		X	X			
PEGPH20 Administration ^q	X		X	X		X		X	X			
Enteric-coated Aspirin Administration for NSCLC subjects ^r	X	X	X	X	X	X	X	X	X			
Enoxaparin Administration for Gastric adenocarcinoma subjects ^r	X	X	X	X	X	X	X	X	X			
Pembrolizumab Administration	Xq					Xq						
Concomitant Therapy/Procedure Recording	X									X	X	
Adverse Event Recording					X					X	X	
Long-Term Follow- up ^c												X

Abbreviations: ALP = alkaline phosphatase; ALT = alanine aminotransferase; AST = aspartate aminotransferase; PEG = PEGylated Recombinant Human Hyaluronidase; CT = computed tomography; D = day; DLT = dose-limiting toxicity; ECG = electrocardiogram; ECOG = Eastern Cooperative Oncology Group;

Halozyme, Inc.

PET = positron emission tomography; DCE-MRI = dynamic contrast-enhanced magnetic resonance imaging; DVT = deep vein thrombosis; HA = hyaluronan; PD = progressive disease; PEGPEM = PEGPH20 + pembrolizumab; PK = pharmacokinetics; T3 = triiodothyronine; T4 = total thyroxine; TSH = thyroid stimulating hormone; Wk = Week; NSCLC = non-small cell cancer.

Note: Visit window is ± 2 days of the specified times.

- ^a See Section 8.2 for details on individual assessments.
- ^b Subjects should return to the study site for an End of Treatment Visit within approximately 7 days after determination of PD or within 7 days after treatment discontinuation of PEGPH20 and pembrolizumab for other reasons.
- c After the End of Treatment Visit, subjects will enter long-term follow-up during which information on the subject's survival and subsequent anti-cancer therapy will be obtained by the site every 12 weeks. Long term follow-up will continue until the subject dies, is lost to follow-up, or withdraws consent.
- ^d Vital signs will be done pre dose on Day 1, Day 8 and Day 15 of all cycles and End of Treatment Visit. On all other days, vital signs will be collected for clinically significant AEs.
- ^e 12-lead ECG will be done at end of treatment and on an as needed basis when clinically indicated.
- f Tumor assessment scans (CT/MRI of chest, abdomen, pelvis, and other areas of known or newly suspected disease) will be obtained and evaluated locally for response evaluation based on Response Evaluation Criteria in Solid Tumors (RECIST) v 1.1 criteria and irRC at the end of Cycle 2, Cycle 4 and then at the end of every fourth treatment cycle thereafter (i.e., Week 3 of Cycles 2, 4, 8, 12, 16 and beyond). Scans will also be sent to the Central Imaging Vendor (CIV) to be stored for possible central review at a later date, if needed. Scans may be obtained any time on or after Day 15 (of Cycles 2, 4, 8, 12, 16 and every fourth treatment cycle thereafter) to allow enough time for the scan to be reviewed locally prior to the subject's next scheduled dosing visit. For subjects who are withdrawn from the study due to clinical disease progression, a CT/MRI scan should be requested as soon as possible after clinical progression is determined.

 g CT/MRI should only be done if radiologic progressive disease was not documented in the previous CT/MRI scan.
- ^h A confirmatory scan should be performed no sooner than 28 days after the initial scan that showed a response based on RECIST v1.1 (PR or CR) or irRC. A confirmatory scan should also be performed to confirm disease progression based on irRC no sooner than 28 days after the initial scan that showed progression.
- ¹ CT/MRI of the brain will be performed for the duration of the study (i.e., post-baseline), if clinically indicated, and within a target of 1 week after a subject achieves a complete response (CR). For NSCLC subjects with a history of treated brain metastases, brain scans will be performed at tumor assessment time points.
- ^j Optional PET/CT will be performed at selected sites. The CIV will analyze PET/CT scans if they are conducted.
- ^k Optional DCE-MRI will be performed at selected sites. The CIV will analyze PET/CT and DCE-MRI scans if they are conducted.
- ¹ On Days 1, 8, and 15 of Cycle 1 and Day 1 of Cycle 2, measurements of total bilirubin, ALP, AST, and ALT (as part of blood chemistry) must be obtained prior to dosing (within 48 hours is acceptable). Local laboratories may be used for these measurements. Dosing can only take place if total bilirubin, ALP, AST and ALT values are within the ranges specified in the Inclusion Criteria. If a subject has any of these values outside the specified ranges on Day 1 of Cycle 2, the Investigator should discuss further dosing plans for the subject with the Sponsor.
- m Blood samples will be collected for testing of thyroid hormones (free T3, free T4, and TSH]) on Day 1 of Cycle 2 and every third cycle thereafter (i.e., Day 1 of Cycles 2, 5, 8, 11, 14, 17, 20, etc.).
- ⁿ Plasma samples for PEGPH20 immunogenicity will be drawn prior to PEGPH20 dosing on day 1 of every cycle and end of treatment.
- Optional post-dose tumor biopsy should be done at the end of Cycle 1 (on or after Day 18) but prior to 1st PEGPH20 dose in Cycle 2.
- Piroxicam (20 mg) will be administered at least 1-2 hours prior to PEGPH20 administration on the day of dosing (timing will be at the Investigator's discretion based on the piroxicam manufacturer's Prescribing Information and subject's convenience), to minimize the severity of MSEs. Prophylactic use of a proton pump inhibitor is mandated for all subjects while receiving PEGPH20 (e.g. 20 mg omeprazole daily or over-the-counter [OTC] equivalent).

- PEGPH20 will be given in increasing doses (1.6, 2.2, 2.6, 3.0 and 4.0 μ g/kg) in combination with 2 mg/kg pembrolizumab in the Dose Escalation portion of the study. If \geq 2 subjects experience a DLT at the 1.6 μ g/kg dose level, Cohort -1 will be opened and subjects will be dosed at 1.0 μ g/kg. In the Dose Expansion portion of the study, PEGPH20 will be given at the RP2D identified in the Dose Escalation portion of the study with 200 mg pembrolizumab.
- All NSCLC subjects will be given enteric-coated 81 mg of prophylactic aspirin/day and all gastric adenocarcinoma subjects will be given prophylactic enoxaparin 40 mg/day (pre-filled syringes of enoxaparin are allowed), for prophylaxis of TE events, given the high incidence seen in these tumor types.

Table 3: Study Schedule of Events: Immunogenicity, Pharmacokinetic, Plasma HA, and Exploratory Biomarker Sample Collection

Sampling	Draw Number	Time Point	Screen	Cyc (21	tment cle 1 days)	Treatment Cycles 2+ (Repeats Every 21 days) Week 1		End of Treatment
				D 1	D2	D1	D2	
Plasma Hyaluronan Exploratory Biomarkers	НА	Screening	X	-	-	-	-	-
PEGPH20 Pharmacokinetics	1	Pre PEGPH20 Dose (within 2 hours prior to dosing)	-	X	1	-	1	-
Plasma Hyaluronan Exploratory Biomarkers Immunogenicity ^a	1HAI	Pre PEGPH20 Dose (within 2 hours prior to dosing)	-	X	-	X	-	-
PEGPH20 Pharmacokinetics	2	15 minutes Post PEGPH20 Dose (±5 minutes)	-	X	-	X	-	-
PEGPH20 Pharmacokinetics	3	1 hour Post PEGPH20 Dose (±15 minutes)	-	X	-	-	-	-
PEGPH20 Pharmacokinetics Plasma Hyaluronan Exploratory Biomarkers	4	2-4 hours Post PEGPH20 Dose	-	X	1	-	-	-
Pembrolizumab Pharmacokinetics	5	Pre PEM Dose (within 2 hours prior to dosing)	-	X	-	X	-	-
PEGPH20 Pharmacokinetics	6	6-8 hours Post PEGPH20 Dose	-	X	-	X	-	-
Plasma Hyaluronan Exploratory Biomarkers	Exploratory 6HA		-	X	-	-	-	-
Pembrolizumab Pharmacokinetics	7	0-2 hours Post PEM Dose	-	X	-	X	-	-

Table 3: Study Schedule of Events: Immunogenicity, Pharmacokinetic, and HA Sample Collection (Continued)

Sampling	Draw Number	Time Point	Screen	Cy (21	tment cle 1 days)	Treatment Cycles 2+ (Repeats Every 21 days) Week 1		End of Treatment
				D1	D2	D1	D2	
PEGPH20 Pharmacokinetics	8	24-26 hours Post PEGPH20 Dose	-	-	X	-	X	-
Plasma Hyaluronan Exploratory Biomarkers	8HA	24-26 hours Post PEGPH20 Dose	-	-	X	-	-	-
PEGPH20 Pharmacokinetics	9	28-32 hours Post PEGPH20 Dose	-	-	X	-	X	-
Pembrolizumab Pharmacokinetics	10	24-28 hours Post PEM Dose	-	-	X	-	X	-
Immunogenicity ^a	99	End of Treatment	-	-	-	-	-	X
PEGPH20 Pharmacokinetics Immunogenicity Plasma Hyaluronan Exploratory Biomarkers Pembrolizumab Pharmacokinetics		Unscheduled	X	X	X	X	X	X

Abbreviations: D = day; HA = hyaluronan; PEM = pembrolizumab.

Notes: Pembrolizumab PK samples will be collected and analyzed when a validated assay is available. If a subject discontinues PEGPH20 therapy, PEGPH20 PK samples will not be collected from that subject. However, if that subject continues on pembrolizumab therapy at the discretion of the Investigator, pembrolizumab PK samples must be collected.

Plasma samples are required for PEGPH20 PK, plasma hyaluronan, biomarker, and PEGPH20 immunogenicity analysis; serum samples are required for pembrolizumab PK analysis.

^a PEGPH20 Immunogenicity.

